10.4 Procedures for verification, validation and securing of electronic clinical data system

The VIEDOC software is installed on a server (secure Data Center) hosted at the VIEDOC company that guarantees the security, maintenance, as well as regular antivirus and firewall updates of this dedicated server. Any modification to the data is tracked, i.e., creation and changes are timestamped, and authors are recorded. Viedoc Technologies complies with the E.U. General Data Protection Regulation (GDPR).

Version: **2.0**; **08** Sep **2021** Page **41** of **61**

Backups are taken, encrypted, and replicated to the paired Microsoft Azure region every five minutes. One full backup for each instance is encrypted and transferred to cold storage in a third location, read back, restored, and tested for integrity every 24 hours.

The VIEDOC electronic system from PCG Solutions is systematically validated at several levels, from program development to actual use in clinical trials:

Unit Test / Code Review

Unit test and code review are validation activities performed by the system developers during the programming phase. Unit tests are written by the programmer while they are writing (or modifying) the source code. Unit tests are automatic test cases. All Viedoc unit tests are automatically executed every time the source code is built. PCG Solutions implements daily builds so these tests are run daily (or more often). The results of the unit testing are reported by the build tool, which is integrated into the PCG Solutions repository. The build automatically fails if any of the unit tests fail, and the source code needs to be corrected and the unit test passed before the next build will pass. Records of all builds are kept in TFS so that the history of the release build of any version of Viedoc can be examined, as well as the builds leading up to that release. The results of the unit testing are summarized in the Validation Report for the release.

Code review is performed by another member of the development team than the programmer of that source code. Code review is mandatory for high-risk implementations and encouraged even for all other source code. Risk evaluation is part of the sprint planning process. Code review is performed either using pair programming or code review sessions where more members of the team are involved. The results of the code review are immediately worked into the source code and are not separately documented.

• Function / System Test

Function and system testing are different names for the same thing at PCG Solutions. The name function test is derived from the fact that the majority of all testing performed at this level is with regards to functional requirements. The name system test simply recognizes that occasionally nonfunctional requirements are also tested (i.e., performance requirements). The same methodology is employed irrespective of whether the requirements are functional or non-functional.

The goal of function testing is to confirm that the implementation fulfils the requirement, i.e., to validate the product implementation against the requirements placed on the product. Function testing is performed by a different member of the system development team than the programmer and consists of exploratory testing and scripted testing.

Exploratory tests are not predefined but are rather focused on testing a given requirement using an approach of simultaneous learning, test design, test execution and test result documentation. Exploratory tests are documented in one test result object in the PCG repository, i.e., the test steps and the test results are documented together and linked to the requirement being tested. Exploratory testing is often performed first in order for the tester to develop a deeper understanding of the requirement before writing the formal scripted tests.

Version: **2.0**; **08 Sep 2021** Page **42** of **61**

Scripted tests are predefined test cases with detailed preconditions, steps to be executed and expected outcomes listed. Scripted test cases are designed and written by one system developer and executed by a different system developer (neither of whom are the programmer who wrote the source code). The results of scripted tests are stored in separate test result objects linked to the test cases in the PCG repository.

All test cases and test results are stored in the PCG repository, and are linked such that test cases are linked to the requirements they test, while test results are linked to the test case they record the results of.

Installation Qualification

The goal of installation qualification is to ensure that the correct versions of all modules that make up a release of the product have been installed correctly on the server. There are two types of installation qualification: Build Installation Qualification and Instance Installation Qualification.

Regarding Built Installation Qualification, when a new product or a new version of a product is to be released, a build for the version is delivered by the development department. Product operations are then responsible for deploying this same build on all production servers. Build installation qualification ensures that the exact content released by the development department (in terms of modules and versions of the modules) and the exact configuration of the server environment (operating system version, database version, other software infrastructure products) are included in the build. This is done by ensuring all software components are in place and of the correct version.

Regarding Instance Installation Qualification, every time a new instance of the product is setup the environment is checked to ensure that all prerequisites are met, and all components are installed.

• Operational Qualification

After completing the Installation Qualification an Operational Qualification is executed to ensure that all core functionality operates as expected. This is performed for every release of a product, and Operational Qualification is documented as part of the release documentation for that release of the product.

Performance Qualification

The goal of performance qualification is to confirm that the delivered product is fit for use, i.e., that the product will work as intended. While function testing will typically find errors where the product implemented does not fulfil the requirement as stated, performance qualification will typically identify weaknesses where the requirements themselves are faulty (for example have been incorrectly analysed or have missed certain conditions).

Performance qualification is scenario-based, designed around using the product in the same way it will be used in a clinical research setting. Performance qualification includes a great deal of regression testing, aimed at ensuring that existing functionality is not affected in new releases. Performance Qualification is performed and documented per release of the product being validated. These documents are stored together with the other release documentation for that product.

Version: **2.0**; **08 Sep 2021** Page **43** of **61**

Build Installation Qualification is performed once for every release of a product, and Instance Installation Qualification is produced once for every instance of the product. Both are documented as part of the release documentation for every release of the product.

10.5 Procedures to maintain and protect subject privacy

It is the responsibility of the sponsor to maintain a security system that prevents unauthorized access to the data, both internally and externally.

Subject privacy is protected through the VIEDOC system at different levels so as to preclude unauthorized access to data:

• Personal data other than medical are limited to a minimum and under full control of the subject.

In the e-Diary, ViedocMe, there is a possibility for the patient to register their email address and/or telephone number to receive reminders, but that information is encrypted within Viedoc and cannot be read by any user. The patient can modify or delete this personal data (the email address and telephone number) at any time. Each patient will have a username and a PIN code randomly assigned for connexion to the e-Diary.

Only authorized persons can access the data.

The permission system is role-based, supporting the principle of least privilege, and restricting access to specific pieces of data to users on a need-to-know basis. Multi-factor authentication, as well as a sophisticated system for delegated provisioning/deprovisioning of user access, provide an additional level of security.

• The risk of data breaches is minimized by full encryption.

In addition to encryption-measures in operations environment (only encrypted endpoints served, encryption-at-rest on disk), encryption-in-transit is enforced through strict-transport-security headers for public endpoints, and sensitive data are encrypted-at-rest in database. The system is also designed to use encryption-in-transit internally between sub-systems.

• External interactions are actively protected.

Viedoc data communication between client and public endpoint is tuned to standards which in turn allows web-application-firewalls to inspect all traffic in prevent mode. Content Delivery Networks (CDN) are not used – all content and client-side code libraries are distributed directly from Viedoc servers, which is also enforced through content-security-policy headers, to ensure authenticity and prevent man-in-the-middle tampering.

Anti-malware signatures are updated in real-time as released by vendor. Web application firewalls are configured with OWASP 3.0 rules in prevent mode. All network segments are protected with firewalls that have block-all by default and only allow whitelisted traffic. Only encrypted endpoints are exposed.

There is a daily review of security bulletins. Each month a black-box vulnerability test (according to PCI-DSS standard) is performed, along with an encryption-in-transit test. A security meeting is held once a month to discuss the current security landscape and review the past month's activity and the plans for the upcoming month.

Version: **2.0**; **08** Sep **2021** Page **44** of **61**

Once a year, a third-party security team is contracted to perform white-box penetration testing of the solution.

10.6 Methods for database locking at the start of analysis and storage upon completion of the clinical investigation

The validated database will be locked upon request of the Data manager following the completion of all steps required, i.e., resolution of all queries, validation of the coding, data review meeting.

10.7 Procedure for data retention

Once the Clinical Investigation Report is signed and validated, the data are archived on a dedicated hard disk file with limited access rights. This specific file is mounted on AXIODIS's OVH server with a back-up every two months as well as copied to an external disk that will be stored under seal within the premises of AXIODIS. The data are conserved for at least 10 years.

Amendments to the CIP 11.

Neither the investigator nor the sponsor may alter the protocol without the authorisation of the other party.

All changes to the protocol are subject to an amendment which must be dated and signed by both parties and must appear as an amendment to the protocol.

Substantial amendments are notified to the EC.

12. **Deviation from Clinical Investigation Plan**

In this context of observational study, the intervention is not protocolized and the study is restricted to the observation of the being of patients during the study. However, we define "Major protocol deviations" as deviations liable to prevent or change the interpretation of the results of the study. The following deviations are considered major:

Non-compliance with the inclusion or exclusion criteria,

 No assessment of the primary efficacy criterion (WURSS-K) at D1, D5±1 and D10±1 during the treatment period,

• Intake of forbidden medication, i.e., nasal irrigation for patients who choose not to take Healsea® children.

All other cases will, a priori, be considered as minor deviations.

All protocol deviations will be managed as per the Standard Operating Procedures of the CRO.

Page **45** of **61** Version: 2.0; 08 Sep 2021

A deviation log shall be maintained by the study sites.

All deviations will be included, as required in the final study report.

Any major deviation from the protocol that has not been previously approved by the sponsor must be reported to the sponsor within 2 working days of the deviation occurrence. Any deviations from the clinical investigation plan that are identified during routine monitoring visits will be reported to the sponsor within 24 hours of being identified.

Corrective and preventive actions and principal investigator disqualification criteria will be described in the monitoring plan.

13. **Device accountability**

Not applicable for an observational study.

14. Ethical consideration

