- **Safety:** All adverse events and incidents will be listed, but only treatmentemergent adverse events/incidents (non-serious + serious)/ undesirable expected side effects will be summarized.

Two groups (called treatment groups) will be extracted from the cohort according to the treatment chosen by the patient.

Adverse events and incidents will be summarized by the number and percentage of patients (by treatment group), classified by System Organ Class and Preferred Term as defined by MedDRA dictionary.

For a given treatment group, a given adverse event will be counted treatment emergent only once per patient during the treatment period.

Frequency and percentage of patients with at least one reported adverse event/ incident/ expected side effect will be tabulated by System Organ Class and by treatment group.

Version: **2.0**; **08** Sep **2021** Page **19** of **61** Study Number: **LPH-2101**

3. Flow Chart

	ACUTE PHASE			FOLLOW-UP			
Visit name	Screening/Inclusion	At home	Telephone call	End of treatment	At home	Telephone call	End of study
Visit Number	V1		TC1	V2		TC2	V3
Days/Weeks	D1	D1 – D10	D5±2	D10±2	D11 – D30±5	D20±2	D30 ± 5
Screening and General Assessments							
Information and consent process	Х						
Eligibility criteria	Х						
Demography and Medical history	Х						
Physical and clinical examination	X			Х			Х
Ongoing medication	Х						
Patient's choice for using Healsea® Children self-administration or not	Х						
Treatment							
Acute phase (Healsea® Children or no saline irrigation as add on therapy)		Х					
Assessments							
Subject e-diary (WURSS-K)		Х			X*		
Adverse Events/incidents/undesirable expected side effects and concomitant medication reporting	Х	Х	Х	Х	х	х	Х

^{*} After D10, the WURSS-K will be assessed once daily until the subject feels not sick for two consecutive days if applicable.

Version: **2.0; 08 Sep 2021** Study Number: **LPH-2101**

4. Identification and description of the investigational Device

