8.2 Investigational device and comparator

The investigational device which is Healsea® Children. This is a CE marked Medical Device. Patients/parents will be allowed to use or not the investigational nasal spray. If they choose nasal symptoms to be treated with Healsea® Children, they will start the nasal spray treatment following

Page **31** of **61** Version: 2.0; 08 Sep 2021

their inclusion visit (Visit 1). Healsea® Children will be used on the top of conventional therapies for common cold and administered with the help of an adult, spraying one puff (1-2 sec) twice a day in each nostril for 10 days.

No comparator is used in this study. Patient/parents who prefer not to use Healsea® Children will use conventional therapies for common cold only. **However, use of nasal irrigation will not be authorized for these patients.**

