8.3.12 Permitted and forbidden concomitant medications

All concomitant medications are authorized except nasal irrigation for patients who do not choose to use Healsea® children.

Version: **2.0**; **08** Sep **2021** Page **36** of **61** Study Number: **LPH-2101**

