9.2 Study population

The study population consists in all the patients included and who do not meet a "major deviation to protocol" as defined in section 12.

The safety population consists in all the patients included in this study.

Version: **2.0**; **08 Sep 2021** Page **38** of **61**

The analysis of primary and secondary endpoints will be performed on study population, safety endpoint will be performed on safety population.

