5. DEFINITION OF THE ANALYSIS SETS

Screened subjects: all subjects who signed an informed consent.

Included subjects: all screened subjects who participated in the study.

Full Analysis Set (FAS): all included subjects who used the investigational medical device at least once.

Per-Protocol (PP) Set: Efficacy population based on the FAS without patients with major protocol deviations.

Safety and Efficacy analyses will be performed on the FAS.

The analyses of the primary and one secondary (modelling of AUC on total WURSS by multivariate ANCOVA) efficacy criteria will also be performed on the PP Set.

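### Protocol and SAP name different primary populations: the protocol's drops comparator children for nasal irrigation, with no time window, and the SAP's FAS wording literally holds no comparator child

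*Protocol*

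**What the plan says.** **Protocol population.** Section 9.2 states: "The study population consists in all the patients included and who do not meet a" major deviation as defined in section 12. It continues: "The analysis of primary and secondary endpoints will be performed on study population". Safety uses all included patients.

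**The deviation.** Section 12 lists three major deviations. Failing an eligibility criterion and lacking the required WURSS-K assessments can happen in either group. The third is "Intake of forbidden medication, i.e., nasal irrigation for patients who choose not to take Healsea® children". Section 8.3.12 gives the matching conduct rule: "All concomitant medications are authorized except nasal irrigation for patients who do not choose to use Healsea® children". Section 8.2 says of children not using the spray that "use of nasal irrigation will not be authorized for these patients". None of these places gives days. SAP 7.2 repeats the deviation, also without days.

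**Flow charts.** In both documents the row "Acute phase (Healsea® Children or no saline irrigation as add on therapy") is marked only under D1-D10.

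**SAP population.** Section 5 defines the FAS as "all included subjects who used the investigational medical device at least once" and states: "Safety and Efficacy analyses will be performed on the FAS". Major deviators leave only the PP Set, on which the primary test and the AUC ANCOVA are repeated (SAP 5, 10.1, 10.2.1). SAP 12, the section for changes to the planned analysis, covers only the definition of symptom duration.

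**The concern.** SAP 6.3.1 treats only the primary criterion as conclusive, and the two documents name different sets of children for it. Under Protocol 9.2, a comparator child who irrigates is removed, while a Healsea child who adds another irrigation stays. Irrigation may be started because symptoms are worse or persist. The removed children may therefore differ in outcome from those who remain, and the removal touches one group only. Treatment is open label and chosen by the family, and Protocol 8.1.2 gives no measures against bias.

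Under the SAP the same removal reaches only the PP analyses, which is the better arrangement. It is not declared as a change, however, and it rests on an FAS definition that cannot be applied literally to a two-group comparison.

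The missing window adds a smaller problem. Read literally, irrigation on D20 would remove a child whose D1-D10 AUC was already complete when it happened.

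**Working it through.** **1. Which children each document analyses**

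| | Protocol 9.2 | SAP 5 and 10.1 |
|---|---|---|
| Primary test | included, no major deviation | FAS, repeated on PP |
| Irrigating comparator | removed | kept in FAS, removed from PP |
| Healsea child adding other irrigation | kept | kept in both |
| Change declared in SAP 12 | – | no |

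Read literally, the FAS contains no comparator child. The two-group test and the FAS mock tables, which have a conventional-therapy column, show that comparators are meant to be in it.

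**2. The plan's own figure**

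Inputs from Protocol 7.4 and SAP 4: 100 per group, standardized effect 0.4, two-sided 5%. The noncentral t gives power 80.4% (99 per group needed by formula). The stated 80% reproduces, so the sample size is not in question.

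**3. If irrigators are removed**

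Assumptions, since the documents give neither an irrigation rate nor irrigators' severity: *k* of 100 comparators are removed, their mean lies *m* SD from the comparator mean, and there is no true difference.

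Shift in comparator mean = *k*/(100 − *k*) × *m*. Standard error = √(1/100 + 1/(100 − *k*)).

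For *k* = 10:
- *m* = 0.5: 10/90 × 0.5 = 0.056 SD
- *m* = 1.0: 10/90 × 1.0 = 0.111 SD
- standard error = √(0.01 + 0.0111) = 0.145

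Two-sided rejection rates by noncentral t:

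| *k* | *m* = 0.5 | *m* = 1.0 |
|---|---|---|
| 5 | 5.4% | 6.5% |
| 10 | 6.7% | 11.8% |
| 20 | 13% | 38% |

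**4. Split by direction**

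If irrigators are sicker, removing them improves the comparator mean and works against Healsea. At *k* = 10, false findings for Healsea fall from the nominal 2.5% to 0.96% (*m* = 0.5) or 0.33% (*m* = 1.0). The rest, 6.7 − 0.96 = 5.7% and 11.8 − 0.33 = 11.5%, is against Healsea. If irrigators are milder, the two tails swap.

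**5. If irrigators are kept**

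Assume a share *p* of comparators irrigate and gain half to all of the 0.4 benefit. The contrast becomes 0.4 × (1 − *p*/2) down to 0.4 × (1 − *p*). At *p* = 10% this is 0.38 down to 0.36.

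| Share irrigating | Power, kept | Power, removed |
|---|---|---|
| 5% | 76.2–78.4% | 79.3% |
| 10% | 71.7–76.2% | 78.2% |
| 20% | 61.5–71.7% | 75.6% |

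The removed column counts only the loss of numbers and assumes irrigators are otherwise typical of their group.

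**The case against.** The strongest reply is that the SAP has already solved the main problem. Protocol 9.1 leaves analysis details to the SAP, and the SAP keeps irrigating comparators in its main analysis. That stands, and it limits the weight of the point. What remains is that Protocol 9.2 still says otherwise, SAP 12 is silent, and the FAS wording does not describe the set intended.

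It can also be said that the asymmetry belongs to the contrast. Conventional therapy without irrigation is the comparator, so irrigation there is crossover, whereas in a Healsea child it is permitted add-on care. This too stands. It supports a PP sensitivity analysis, but not removal from the primary test.

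On the window, the flow charts point to D1-D10, and the data review meeting validates deviation status before database lock (SAP 7.2, Protocol 10.3). That narrows the gap, but it leaves the decision to be made case by case with diary data in hand and treatment known.

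A reader might infer that the exclusion favours Healsea. The documents do not support that. The only mechanism that suggests itself, irrigation because of worse symptoms, pushes the other way, and the two-sided rates of 6.7% to 11.8% must not be read as false claims of benefit. A reader might also infer that the SAP means to leave comparators out of the FAS; its mock tables show the contrary.

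**Conclusion.** The point holds as a conflict between the documents with a one-group exclusion inside it. Under Protocol 9.2 the exclusion enters the primary test; under the SAP it enters only the PP analyses of the AUC. The FAS definition needs replacing whichever population is chosen.

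Neither size nor direction can be derived from the documents. On the assumed range, the bias is small unless about 10 or more comparator children irrigate: at 5 removed the two-sided rate is at most 6.5%. The results rest on equal groups of 100, a t-test, no true difference for the error rates, and irrigators lying 0.5 to 1.0 SD from their group mean. This should be corrected because the correction is cheap and concerns the one conclusive test; it is not evidence that the SAP's main analysis is biased.

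**What to change.** 1. In Protocol 9.2 and SAP 5, state that the primary analysis takes all included children in both groups, classified by the choice recorded at Visit 1, with the AUC computed as in SAP 6.4.6. Replace the FAS definition to match, keep the PP Set as a sensitivity analysis, and list the change of population in SAP 12.
2. In Protocol 12 and SAP 7.2 only, count nasal irrigation in a comparator child as a major deviation when it is used during D1-D10. Leave Protocol 8.2 and 8.3.12 as they are. A window there would expressly permit comparator irrigation on D11-D30, while symptom duration, complications needing antibiotics, cold medication and family spread are still being measured.

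No separate table of comparator irrigation is needed, because SAP 7.2 already describes deviations by group and lists each one.

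The cost is wording in four sections (Protocol 9.2 and 12, SAP 5 and 7.2) plus one entry in SAP 12; no new data are required. There are two statistical costs. Keeping irrigators may dilute the effect: at an assumed 10%, power is 71.7–76.2% kept against 78.2% removed. Children who chose Healsea but never used it also stay in their group. Children without a D1 score still drop out, because SAP 6.4.6 gives them no AUC.
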